10.4. Blinding

Blinding/unblinding processes will be dictated by the parent study from which the participants are coming. Both study staff and participants will be blinded to the random assignments of participants assigned to study treatment groups that include a study product. However, the assignment of participants to the no treatment group (e.g. condom only arm in HPTN 035) cannot be blinded. Randomization documentation and other pharmacy records must not be accessible to study staff members who complete other study procedures with participants.

Blinding will be maintained until all data are entered into the parent study database, all study endpoint data and other data included in the final analysis have been cleaned and verified, and the data are ready for final analysis in the parent study. Unblinding of data will only occur after the unblinding of the data in the parent study. This will be explained to participants as part of the study informed consent process.

There are no circumstances under which it is expected that unblinding will be necessary for the provision of medical treatment or to otherwise protect the safety of study participants. If an Investigator feels that specific product knowledge is necessary to protect participant safety, the Investigator will notify the Protocol Chair, Protocol Biostatistician, and DAIDS Medical Officer (or designees) to consider and jointly rule upon the request.

10.5. Participant Accrual and Retention

All seroconverters, regardless of their seroconversion date, from the ongoing HPTN 035 and 059 trials will be recruited into this study. Although some of these participants would have seroconverted more than a year ago, which would make them ineligible for the primary objective of this study, those participants could be used in the assessment of some of the secondary objectives. All newly identified seroconverters during follow-up in HPTN 035 and 059 will be recruited for this study.

Once a participant has enrolled in the study, the study site will make every reasonable effort to retain her for the entire study period. A maximum of 5% annual loss-to-follow-up of enrolled participants is targeted.

10.6. Data and Safety Monitoring and Analysis

10.6.1. Study Monitoring Committee (SMC)

No Data and Safety Monitoring Board (DSMB) oversight is planned for this observational study. The MTN SMC will conduct interim reviews of study progress (blinded to treatment assignment), including rates of participant accrual, retention, completion of primary and main secondary endpoint assessments, and study or lab issues. These reviews will take place approximately every 4-6 months, or as needed. At the time of these reviews, or at any other time, the SMC may recommend that the study proceed as designed, proceed with design modifications, or be discontinued. The SMC may consider recommending termination of this study if recruitment and retention are lower than targeted, or if study data quality is poor.

10.6.2. Data Analysis

Primary Analyses

Descriptive analyses of the seroconverters will include calculation of the mean and median viral load by active microbicide and placebo/control groups. A simple t-test can be used to compare log-transformed viral load levels between these two groups. However, caution must be exercised in the interpretation of any difference (or lack of difference) found. Although the overall active microbicide and placebo/control groups should be comparable at baseline (in the parent study) due to randomization, individuals who seroconvert in the active microbicide group may not be comparable to individuals who seroconvert in the placebo/control group. Approaches described by Gilbert et al, *Biometrics*, 2003 will be used for isolating the effect of an intervention on post-seroconversion outcomes.^{xvi} Furthermore, the primary analysis will be restricted to

seroconverters that have not initiated ART in the first 12 months after seroconversion.

Linear regression using the log-transformed viral load levels as the outcome and baseline or other covariates (e.g. CD4+ T-cell) will be used to compute adjusted differences between the active microbicide and placebo/control groups. The interpretation of these adjusted differences is subject to the same cautions noted above.

Sub-group exploratory analyses will be performed to explore difference between type of products and type of controls. Mainly, seroconverters will be grouped by the type of intervention received: (1) PRO2000, (2) BufferGel, (3) Placebo gel, and (4) Condom only.

Secondary Analyses

Secondary analyses of CD4+ T-cell counts will be virtually identical to those described for viral load levels above, although it is typically not necessary to log-transform CD4+ T-cell levels to obtain valid inferences. Descriptive statistics will be used to characterize overall CD4+ T-cell levels and levels within subgroups. T-tests and linear regression will be used to obtain unadjusted and adjusted estimates of the treatment effect. Again, the interpretation of these differences is subject to the same cautions noted above for the primary analyses.

Many other secondary analyses will be performed using the secondary endpoints described in Section 10.2.2. Time-to-event secondary endpoints will be analyzed according to the Kaplan-Meier method where differences between groups will be tested using the stratified log-rank test while secondary endpoints involving repeated assessment over time (e.g. sexual behavior) will be compared at selected time points. At each of the selected time points, comparison of the two groups will be made using Fisher exact test or Wilcoxon rank-sum test as appropriate. More generally, GEE (Generalized Estimating Equation) methods and robust variance estimates will be used to evaluate group.

Data on behaviors that are associated with HIV-1 transmission such as sexual intercourse without a condom, the frequency of sexual intercourse, and the numbers of sexual partners will be measured over time among women in this study and compared to the same behaviors reported by women in ongoing microbicide trials (including parent trials) who are HIV-1 negative and to large household surveys of women (Demographic Health Surveys) in the same countries as the women in this study are located.

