2.2. Study Hypothesis and Rationale

2.2.1. Study Hypothesis

Exposure to study agents in MTN clinical trials will not impact the natural history of HIV-1 infection as measured by the virologic, immunologic and clinical outcomes of participants with HIV-1 seroconversion during microbicide trials.

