4. STUDY DESIGN

4.1. Identification of Study Design

MTN-015 is a multi-site, prospective observational cohort study. Potential participants will be offered enrollment in MTN-015 following identification of HIV-1 seroconversion in the parent trial (the trial from which they were identified). For the purposes of this protocol, date of seroconversion is defined as the date of HIV-1 seroconversion used in the parent trial. The participant's HIV-1 seroconversion should be confirmed according to the HIV-1 testing algorithm of the parent trial. Study participants may be followed concurrently in the MTN parent trial and MTN-015 for the duration of the parent trial and subsequently continue in MTN-015 for the duration of MTN funding. Participants in MTN-015 may participate in other clinical trials including HIV-1 treatment trials.

This study will utilize two follow-up visit schedules: one based on the date of identification of seroconversion in the parent study and one based on initiation of ART use; see Section 7 for details on each schedule. Participants who have not initiated use of ART at the time of enrollment in MTN-015 will follow the schedule based on the date of identification of seroconversion. Participants who have initiated use of ART at the time of enrollment in MTN-015 will follow the schedule based on the date of ART initiation. Participants who initiate use of ART during follow-up in MTN-015 will have their follow-up schedule adjusted to the schedule based on initiation of ART use. Study sites will be provided with computerized tools (either spreadsheet or web-based) to assist them in determining the appropriate visit schedule to follow for each participant. Past or current use of most ART regimens will constitute initiation of ART for purposes of this study; however, use of single dose nevirapine for PMTCT will not constitute initiation of ART for purposes of this study.

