7.1. Screening and Enrollment Visit

Table 1: Screening and Enrollment Visit

Screening and Enrollment Visit	
Component	Procedure/Analysis
Administrative: Screening	Informed Consent Review Parent Study Records to Confirm HIV-1 Seroconversion Eligibility Determination
Administrative: Enrollment	Assign Participant ID Update Locator Information Update Demographics Schedule Next Visit Reimbursement
Clinical	Update Medical History Record Clinical Events Acute Seroconversion Assessment Concomitant Medications Assessment *Antiretroviral Treatment Record Complete Physical Exam (See Appendix IV) Gynecologic Exam (See Appendix IV) *Provide Test Results *Treatment or Referral
Behavioral	Baseline Behavioral Questionnaire *Adherence Questionnaire STI Risk Reduction and Contraception Counseling HIV Secondary Prevention Counseling Provision of Condoms
Urine	Qualitative hCG SDA for Chlamydia and Gonorrhea
Blood	Complete Blood Count Liver and Renal Function Tests Syphilis Serology CD4+ T-Cell Count Plasma HIV-1 RNA HIV-1 Genotypic Resistance Test (MTN NL, archived plasma) HSV-2 Antibody (site lab, regional lab, or MTN NL, archived plasma) HIV ELISA and Western Blot (MTN NL, archived serum)**
Pelvic Samples	Vaginal pH Wet Mount for bacterial vaginosis (BV), Candida, and Trichomonas †Pap Smear at Selected Sites
Specimens for Storage	Vaginal Swabs Cervicovaginal Lavage Plasma Serum Peripheral Blood Mononuclear Cells (PBMC)

*If indicated, **If not previously confirmed in a Network Laboratory, † PAP smears should be done at 6 month intervals in the first year after seroconversion, and then annually if the initial tests are negative.

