10.2. Study Endpoints

10.2.1. Primary Endpoint

Virologic Response

Consistent with the primary study objective, plasma HIV-1 RNA 12 months after identification of HIV-1 seroconversion will be the primary endpoint. Comparison of the plasma HIV-1 RNA level 12 months after HIV-1 seroconversion between active microbicide and placebo/control groups is the primary objective of this study.

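### The only covariate named for the adjusted 12-month viral-load comparison is CD4+ count, which this protocol measures only after infection and product exposure and also treats as an outcome

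*Protocol*

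**What the plan says.** The primary endpoint is a single quantity: "plasma HIV-1 RNA 12 months after identification of HIV-1 seroconversion will be the primary endpoint" (Protocol 10.2.1). Section 10.6.2 lists three pieces under the primary analyses.

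- **Unadjusted comparison:** "A simple t-test can be used to compare log-transformed viral load levels between these two groups".
- **Sensitivity approach:** a cited method for post-infection outcomes, brought in because women who seroconvert on active product may differ from those who seroconvert on control.
- **Adjusted comparison:** "Linear regression using the log-transformed viral load levels as the outcome and baseline or other covariates (e.g. CD4+ T-cell) will be used" to obtain the group differences after adjustment. CD4+ is the only covariate given by name. No time point is attached to it.

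On when CD4+ is measured, section 4.1 says: "Potential participants will be offered enrollment in MTN-015 following identification of HIV-1 seroconversion in the parent trial". Section 5 sets no limit on the delay. The first CD4+ count is at the Screening and Enrollment visit, where Table 1 lists it among the blood tests: "Syphilis Serology CD4+ T-Cell Count Plasma HIV-1 RNA HIV-1 Genotypic Resistance Test". All later counts (Tables 2 to 6, Appendix I) follow that visit. The protocol describes no pre-infection CD4+ value.

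CD4+ is also an outcome. The hypothesis in 2.2.1 concerns product effects "as measured by the virologic, immunologic and clinical outcomes of participants with HIV-1 seroconversion during microbicide trials". The first secondary objective (3.2) compares CD4+ trajectories by assignment, and 10.2.2 compares time to CD4+-defined immunologic failure between the same groups.

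**The concern.** A covariate in a model for a treatment effect should not be something the treatment can change. By the protocol's own account, CD4+ is something the product may change. Section 2.1 also gives a route: a product may lower the viral set point, and slower disease progression may follow. A CD4+ count taken after infection can then carry part of the product effect. Holding it fixed in the viral-load model would remove that part.

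The caution in 10.6.2 does not cover this. It concerns who becomes infected in each group, and it is carried over unchanged to the adjusted differences. A reader warned that the groups may not be comparable may put more weight on the adjusted figure, so its meaning matters. If it is smaller than the unadjusted figure, nothing in the text would tell the reader whether imbalance was corrected or product effect was removed.

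**Working it through.** **Inputs from Protocol 10.3 and Table 7.** Between-person variance 0.52; within-person variance 0.096; 46 active and 92 control; two-sided alpha 0.05; difference d = 0.4 log10. The CD4+/viral-load correlation rho is not in the documents. I assume absolute values of 0.3 to 0.5.

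**Step 1: reproduce the plan's figure.**
- Variance for one observation = 0.52 + 0.096 = 0.616, so SD = 0.785.
- SE = 0.785 × √(1/46 + 1/92) = 0.1417.
- Power = Φ(0.4/0.1417 − 1.96) = 80.6%, or 80.0% with the noncentral t.

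The protocol states 80%, so the figure reproduces. It describes an unadjusted two-group comparison.

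**Step 2: general form.** Let A be the group, V the 12-month log viral load and C the CD4+ count. The adjusted group coefficient is

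d − β × (difference in mean C between groups),

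where β = rho × SD(V)/SD(C) is the within-group slope of V on C. Everything depends on whether, and by what route, the groups differ in C.

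**Step 3: CD4+ responds to the product only through viral load.** Let V = dA + e and C = −bV + u. Then rho is negative, b = |rho| × SD(C)/SD(V), and the group difference in C is −b × d. Substituting gives an adjusted coefficient of d × (1 − rho²). The residual SD becomes SD × √(1 − rho²), so power = Φ(0.4 × √(1 − rho²)/0.1417 − 1.96).

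| assumed absolute rho | expected adjusted difference | share lost | power of adjusted test |
|---|---|---|---|
| 0.3 | 0.4 × 0.91 = 0.364 | 9% | 76.8% |
| 0.4 | 0.4 × 0.84 = 0.336 | 16% | 73.5% |
| 0.5 | 0.4 × 0.75 = 0.300 | 25% | 68.6% |

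A simulation of 10,000 trials with 46 and 92 women gave mean adjusted differences of 0.365 (rho 0.3) and 0.301 (rho 0.5), with power 76% and 67%.

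**Step 4: CD4+ is prognostic only.** Suppose the same correlation comes entirely from host factors or pre-infection CD4+ level, which the product does not change. The groups then do not differ in mean C, the coefficient stays at 0.40, and only the residual SD shrinks. Power = Φ(0.4/(0.1417 × √(1 − rho²)) − 1.96), which is 84%, 87% and 90% for rho 0.3, 0.4 and 0.5.

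**Step 5: other routes.** If the product also acts on CD4+ by a path that does not run through viral load, the group difference in C can have either sign. By the formula in Step 2, the adjusted difference can then be too small or too large. If host factors affect both markers while the product affects CD4+, the sign is likewise not fixed.

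**The case against.** The strongest reply has four parts.

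**CD4+ is only an example.** No time point is fixed and no final model is committed to. The covariate list may properly be settled in an analysis plan that is not shown. Section 10.6.2 also allows baseline covariates and, in the same passage, uses baseline for the parent study. This stands in part: the text permits a sound choice. But the one choice it names is unsuitable if taken from any count in this protocol's schedule, and no earlier count is described.

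**The main comparison is untouched.** A reader might infer that the study loses power or that its primary result is biased. The documents do not support that. The t-test and the sensitivity approach do not use CD4+, and Table 7 reproduces without it. The lower power figures in Step 3 belong to the adjusted model alone.

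**The direction of bias is not established.** A reader might infer that adjustment always pulls the difference toward zero, in line with the study's no-effect hypothesis. That holds only under Step 3. An enrollment CD4+ count that precedes the 12-month sample cannot be caused by that sample. It would have to reflect product-shifted viral load already present by then, and the documents do not say how much of the correlation arises in that way. If the product affects neither marker, there is nothing to remove. This objection stands, and it is why the size is given as conditional.

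**No covariate is named for the CD4+ model.** Section 10.6.2 describes that analysis as nearly the same as the viral-load one, and a reader might infer that viral load would enter it. The text does not say so.

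**Conclusion.** The point holds in limited form. As worded, 10.6.2 invites adjustment of the primary outcome for a variable that is measured after exposure and that the protocol itself studies as a possible effect of exposure. The resulting difference need not estimate the contrast in the primary objective.

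If CD4+ responds to the product only through viral load, a true 0.40 log10 would be estimated as about 0.36 to 0.30 at assumed absolute correlations of 0.3 to 0.5. Section 10.3 presents 0.4 as about the smallest change likely to matter for disease progression, so the adjusted estimate would on average fall below that mark. If CD4+ is purely prognostic there is no bias and some gain in precision. With other pathways the bias could go either way. The protocol gives no means of telling these cases apart, and that is the reason not to name CD4+ here. This is a worthwhile correction to a secondary layer of the primary analysis, not a fault in the study's main test or its sample size.

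**What to change.** In 10.6.2, make three changes to the sentence on linear regression and what follows it.

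1. Replace the CD4+ example with covariates fixed before infection: for example parent trial, site, age and other parent-trial baseline variables where available.
2. State that no variable measured after seroconversion, including CD4+ count and enrollment viral load, enters the adjusted primary model.
3. If a CD4-adjusted model is still wanted, state which count is used and when it is taken, and label the model exploratory, with a note that its group coefficient is not the overall product effect.

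The cost is a sentence or two of text, with no new visits or assays. Access to parent-trial baseline variables should be confirmed, because the protocol itself mentions only a review of parent records to confirm seroconversion and an update of demographics. The statistical downside is a possible loss of precision: if CD4+ were only prognostic, the adjusted model would give up the gain in Step 4 (power of 84% to 90%, against 80.6% unadjusted).

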3.2. Secondary Objectives

- To characterize the trajectory of CD4+ T-cell counts after HIV-1 seroconversion among antiretroviral treatment naïve participants assigned to an active microbicide or chemoprophylactic agent compared to control participants.
- To compare the plasma HIV-1 RNA level six months after HIV-1 seroconversion among antiretroviral treatment naïve participants assigned to an active microbicide or chemoprophylactic agent compared to control participants.

- To evaluate the prevalence of HIV-1 drug resistance mutations in plasma and genital tract specimens after HIV-1 seroconversion among participants assigned to an active microbicidal or chemoprophylactic agent compared to control participants.
- To evaluate the virologic response to initiation of antiretroviral therapy among participants assigned to an active microbicidal or chemoprophylactic agent compared to control participants in microbicide trials and by study specific analysis (for larger trials including current and future trials).
 - The proportion with HIV-1 RNA less than 50 copies/mL six months, twelve months, and twenty-four months following initiation of antiretroviral therapy
- To describe the CD4+ T-cell response to initiation of antiretroviral therapy in participants after seroconversion in microbicide trials.
 - The CD4+ T-cell increase six months, twelve months, and twenty-four months following initiation of antiretroviral therapy
- To compare the HIV-1 drug resistance profile, among antiretroviral therapy recipients, at the time of virologic failure (HIV-1 RNA >200 copies/mL at or after six months of antiretroviral therapy) in participants assigned to an active microbicidal or chemoprophylactic agent compared to control in microbicide trials and by study specific analysis (for larger trials including current and future trials).
- To evaluate the prevalence and persistence of HIV drug resistance mutations in plasma and cervical lavage fluid using more sensitive methods (which may include modified ultrasensitive assays of plasma HIV RNA) in study specific subgroups of seroconverters.
- To describe HIV-1 related (WHO Stage II) and AIDS-defining (WHO Stage III and IV) clinical events and deaths (from any cause) occurring among seroconverters with and without antiretroviral therapy.
- To compare the rate of HIV disease progression among participants assigned to an active microbicidal or chemoprophylactic agent compared to control.

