10.2.2. Secondary Endpoints

Consistent with the secondary study objectives, the following secondary endpoints will be assessed:

- **Immunologic response. (CD4+ T cell count).** CD4⁺ T cell counts at Weeks 0 and 2, Months 1, 3, 6 and every 6 months thereafter. Time from seroconversion to immunologic failure will be compared between active microbicide and placebo/control groups. Immunologic failure is defined as two consecutive measurements of CD4+ T-cell count within or below the range of 200-250 cells/mm³, or the development of an AIDS defining illness.
- **Virologic and immunologic responses (CD4+ T-cell count) after initiation of ART.** CD4+ T-cell count and blood plasma HIV-1 RNA levels over time after initiation of ART. Time from initiation of ART to immunologic and virologic failure.
- **HIV-1 related and AIDS-defining events.** Occurrence and frequency of HIV-1 related and AIDS-defining events. Time from enrollment to time of first AIDS-defining event or death.
- **Sexual behavior, partnership status, and occurrence of social harms.** Sexual behavior over time following seroconversion at Months 0, 3, 12, and 24 months. Participants who enroll ≥3 months after seroconversion will be followed at 12 months and 24 months only.
- **HIV-1 genotypic mutations and drug resistant virus.** Prevalence of HIV-1 genotypic mutations over time and drug resistant HIV-1 virus in plasma and genital tract. Proportions of infected participants acquiring a drug resistant HIV-1 virus.

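### The failure endpoints leave out death, so under Kaplan-Meier and log-rank they compare cause-specific failure only, and 1 minus Kaplan-Meier overstates the risk of failure

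*Protocol*

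**What the plan says.** **Method (Protocol 10.6.2).** One sentence covers every time-to-event secondary endpoint: "Time-to-event secondary endpoints will be analyzed according to the Kaplan-Meier method where differences between groups will be tested using the stratified log-rank test". No rule is given for a death that occurs before the event of interest.

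**Immunologic failure (10.2.2).** The laboratory criterion needs two low CD4+ counts in a row, with the threshold given as a band between 200 and 250 cells/mm³. The clinical alternative is worded "or the development of an AIDS defining illness". Death is not part of it. The comparison is between groups: "Time from seroconversion to immunologic failure will be compared between active microbicide and placebo/control groups".

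**Failure after ART (10.2.2).** "Time from initiation of ART to immunologic and virologic failure". Section 10.2.2 does not itself define virologic failure. The only definition in the protocol is in the drug-resistance objective in 3.2, repeated in the Protocol Summary: "HIV-1 RNA >200 copies/mL at or after six months of antiretroviral therapy". Death is not part of that either.

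**The endpoint that counts death (10.2.2).** "Time from enrollment to time of first AIDS-defining event or death". It falls under the same Kaplan-Meier and log-rank sentence. Section 3.2 also has a descriptive objective covering deaths from any cause.

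**The concern.** When death is not an event, a standard Kaplan-Meier analysis has only one place to put a woman who dies first: she is censored at death. Two consequences follow.

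- The log-rank test compares the rate of failure among women still alive and free of failure. Extra deaths in one group do not move it.
- 1 minus Kaplan-Meier estimates failure in a setting where nobody dies, which is higher than the proportion who actually fail.

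The choice is odd for immunologic failure, because that endpoint already takes in clinical progression (an AIDS-defining illness) but stops short of its worst form. On the ART clock, if the definition from 3.2 is carried over, virologic failure cannot be scored before six months, so a death in that period can never count as failure.

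What is at stake is interpretation. The study hypothesis in 2.2.1 is one of no effect on natural history. Equal failure curves could be read as equal progression when they say nothing about deaths without prior failure.

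**Working it through.** **1. Is there a plan figure to reproduce?** Not for this point. The protocol gives no event count, hazard ratio, failure rate or death rate for the time-to-event endpoints. Its power table (Table 7) concerns the 12-month viral load and does not bear on it.

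**2. Which clocks count death?**

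| Endpoint | Clock starts | Counts AIDS illness | Counts death |
|---|---|---|---|
| Immunologic failure | seroconversion | yes | no |
| Immunologic failure after ART | ART initiation | yes | no |
| Virologic failure after ART | ART initiation | no | no |
| AIDS event or death | enrollment | yes | yes |

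Section 5 sets no limit on the time from identified seroconversion to enrollment, so the last clock can differ materially from the first. No row with an ART clock counts death.

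**3. How can a woman die without a scored immunologic failure?** She needs no recorded AIDS-defining event (WHO Stage III or IV, per 3.2) and no second consecutive low count. After Month 6, visits are six months apart. Windows are contiguous (7.2: Month 24 runs from Month 21 through Month 27), so two consecutive counts can lie nearly 12 months apart.

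**4. Illustration. All rates are assumptions.** Constant hazards: failure λ per year, equal in both groups; death without prior failure μ per year, twice as high in the active group; T = 3 years. Group sizes of 92 control and 46 active come from 10.3.

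- Kaplan-Meier failure, deaths censored: 1 − exp(−λT)
- Cumulative incidence of failure: λ/(λ+μ) × [1 − exp(−(λ+μ)T)]
- Failure or death: 1 − exp(−(λ+μ)T)
- Hazard ratio for failure or death: (λ+μ_active)/(λ+μ_control)

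Worked case, λ = 0.10, μ = 0.01 versus 0.02:
- Kaplan-Meier: 1 − exp(−0.30) = 25.9% in both groups, hazard ratio 1.00.
- Cumulative incidence: 25.6% control, 25.2% active.
- Failure or death: 1 − exp(−0.33) = 28.1% versus 1 − exp(−0.36) = 30.2%; hazard ratio 0.12/0.11 = 1.09.
- Deaths without failure: 92 × (0.01/0.11) × 0.281 = 2.4 control; 46 × (0.02/0.12) × 0.302 = 2.3 active.

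Range (control / active):

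| λ | μ | Kaplan-Meier | Cumulative incidence | Failure or death | Hazard ratio, failure or death |
|---|---|---|---|---|---|
| 0.20 | 0.005 / 0.01 | 45.1% both | 44.8% / 44.5% | 45.9% / 46.7% | 1.02 |
| 0.05 | 0.005 / 0.01 | 13.9% both | 13.8% / 13.7% | 15.2% / 16.5% | 1.09 |
| 0.10 | 0.01 / 0.02 | 25.9% both | 25.6% / 25.2% | 28.1% / 30.2% | 1.09 |
| 0.20 | 0.05 / 0.10 | 45.1% both | 42.2% / 39.6% | 52.8% / 59.3% | 1.20 |
| 0.05 | 0.05 / 0.10 | 13.9% both | 13.0% / 12.1% | 25.9% / 36.2% | 1.50 |

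In the worked case, 1 minus Kaplan-Meier overstates failure by less than 1 percentage point. In the rows shown the overstatement reaches 45.1 − 39.6 = 5.5 points, at the highest death rate.

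**The case against.** **No censoring rule is stated, and such rules are commonly left to a statistical analysis plan.** It is true that censoring at death is an inference. But it follows from definitions and a method that the protocol does fix, so an analysis plan faithful to this text would inherit it.

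**Deaths are already compared between groups.** This stands in large part. A reader might infer that an excess of deaths goes unnoticed; the AIDS-event-or-death endpoint shows otherwise. Nor does the protocol contradict itself by counting deaths in one endpoint and not in another: these are different questions. What remains is that the endpoint with deaths runs from enrollment and has no counterpart on the ART clock.

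**The gap for immunologic failure is narrow.** This also stands. A Stage III or IV event before death already counts as failure, and clinical events are updated at every scheduled visit. Only deaths without such an event and without two low counts are affected.

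**The log-rank test is not wrong.** Correct. With death censored it validly compares cause-specific hazards. A reader might infer that the test is invalid because women close to failure are also more likely to die. That dependence undermines a reading of the curves as risk without death, not the cause-specific comparison.

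**These endpoints do not carry the main objectives.** Largely right. Section 3.2 measures virologic response to ART as the proportion below 50 copies/mL at fixed times, and does not tie the disease-progression objective to immunologic failure alone.

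**A composite would rarely detect the difference.** Also right. In the worked case there are about 92 × 0.281 + 46 × 0.302 = 39.8 events, so the expected log-rank z is about ln(1.09) × √(39.8 × 2/9) = 0.26, against 1.96 for significance. The case for change rests on clear interpretation, not on power.

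**Conclusion.** The point holds in a limited form. As written, the two failure endpoints omit death, and the stated method leaves censoring as the only place for a death without prior failure. The test is then cause-specific, and 1 minus Kaplan-Meier is too high as a probability of failure.

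The size cannot be derived from the protocol. Under the assumed rates, with twice the deaths in the active group and no difference in failure, the planned comparison shows 1.00 where failure-or-death shows 1.02 to 1.50. The upper end needs 5 versus 10 deaths per 100 person-years; at 1 versus 2 it is about 1.1, with two or so such deaths per group. The effect is probably small.

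The statement that virologic failure cannot be scored in the first six months of ART depends on carrying the 3.2 definition over to the time-to-event endpoint. All of this concerns secondary endpoints; priority is low to moderate.

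**What to change.** **In 10.2.2:** add death from any cause to the immunologic failure endpoint. Show the components (low counts, AIDS-defining illness, death) and keep the present definition as a sensitivity analysis.

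**In 10.6.2:**
- Report immunologic failure under its present definition, and virologic failure, as cumulative incidence with death as a competing event, instead of 1 minus Kaplan-Meier.
- Describe the log-rank test on those definitions as a cause-specific comparison, to be read beside the AIDS-event-or-death result.
- Use virologic failure or death as a sensitivity analysis only. Making it the main endpoint would mix treatment response with mortality, which is a trade-off and not a clear gain.

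**Cost:** some wording and a few lines of code. Deaths are already needed for another secondary endpoint, so no new data are collected. The downside is that deaths unrelated to HIV add some noise to the immunologic composite; showing the components makes this visible.
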